5.2.2.2 Microbiologic Outcomes

Microbiological response definitions for the evaluations performed at the EOT and PTE Visits and analyzed in the microITT and ME populations are presented in the table below. Post-baseline microbiological samples will be collected only as clinically indicated. Atypical pathogens identified only by acute and convalescent serology or baseline urinary antigen tests (UAT), and *Streptococcus pneumoniae* identified only by baseline UAT can only have a presumed or indeterminate microbiologic response.

If a subject has the same pathogen (ie, same genus and species) identified from both a respiratory and blood specimen, a microbiological response is determined for each of the pathogens. The microbiologic response for the respiratory pathogen is based on the pathogen isolated from the EOT or PTE specimen, if a specimen was collected. The microbiologic response for the blood pathogen is based on the blood sample collected at EOT or PTE, or if a sample was not collected at the post-baseline visit, the blood sample collected prior to and closest to the visit. For the pathogen specific microbiologic response, the worst outcome for the pathogen should be summarized. If *Streptococcus pneumoniae* is identified from both a UAT and a culture, the culture should be used to determine microbiological response.

Table 4. Per-Pathogen Microbiological Response Definitions at the EOT and PTE Visits

Term	Definition
Eradication	The baseline pathogen based on culture was absent from repeat culture(s) of the same sample type (blood or respiratory specimen).
Presumed Eradication	No post-baseline source specimen to culture in a subject assessed with a clinical success by the Investigator
Persistence	The baseline pathogen based on culture was present in repeat culture(s) of the same sample type (blood or respiratory specimen).
Presumed Persistence	No post-baseline source specimen to culture in a subject assessed with a clinical failure by the Investigator
Indeterminate	The subject's clinical response is indeterminate or other circumstance that precludes a microbiological evaluation

Abbreviations: EOT = end of treatment; PTE = post-therapy evaluation.

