Staphylococcus aureus will be considered a distinct pathogen with methicillin-resistant *Staphylococcus aureus* (MRSA) and methicillin-susceptible *Staphylococcus aureus* (MSSA) considered distinct pathogens. Likewise, *Streptococcus pneumoniae* will be a distinct pathogen with penicillin-nonsusceptible *Streptococcus pneumoniae* (PNSSP), penicillin-susceptible *Streptococcus pneumoniae* (PSSP), macrolide-resistant *Streptococcus pneumoniae*, quinolone-resistant *Streptococcus pneumoniae*, and multiple drug resistant *Streptococcus pneumoniae* (MDRSP) each considered distinct pathogens. A pathogen will be considered multiple drug resistant if susceptibility testing shows resistance to 3 or more of the classes of antibiotics provided below except in the case of MRSA where penicillin and cephalosporin are due to a single mechanism in which case 2 non- β -lactam resistances in addition to oxacillin, will be considered multi-drug resistant. *Streptococcus* spp. and *Staphylococcus* spp., isolates resistant to macrolides but susceptible to lincosamides and D-test positive ($> 4/0.5$ ug/ml) will be considered resistant to both macrolides and lincosamides. Susceptibility will be based on the most current CLSI guidelines for each antibiotic or if unavailable, on FDA labeled susceptibility criteria. Antibiotics that define resistance for the class are listed as follows:

- Penicillins – penicillin
- Fluoroquinolones – moxifloxacin
- Cephalosporins – ceftriaxone
- Lincosamides – clindamycin
- Macrolides – azithromycin or erythromycin
- Tetracyclines – tetracycline or doxycycline
- Folate Pathway Inhibitors – Trimethoprim/sulfamethoxazole
- Glycopeptides – vancomycin
- Oxazolidinone – linezolid

If there are multiple specimens (of the same testing modality) from the same time-point where the same pathogen is isolated, only the pathogen with the highest MIC to the test article received will be used. If the pathogens have the same MIC to the test article received, the pathogen with the lowest accession number will be used. The Gram's stain associated with the selected pathogen will be utilized for analysis.

If the same pathogen is identified from the blood and respiratory sample, for tables providing MIC or disk diffusion data, the pathogen with the highest MIC to the test article received will be used.

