The pathogenic organisms identified from the baseline blood culture, culture of the respiratory specimen, UAT, and serology will be presented by genus and species and by testing modality (ie, culture, UAT, serology) for *Streptococcus pneumoniae* and *Legionella pneumophila*, for the microITT, expanded microITT, ME-EOT, and ME-PTE populations. The same pathogen identified from multiple testing modalities will be counted only once in the summary at the genus and species level. The pathogenic organisms identified from the baseline blood culture, culture of the respiratory specimen, UAT, and serology will also be presented by geographic region in the microITT population. The number and percentage of subjects with CABP caused by monomicrobial and polymicrobial Gram-positive or Gram-negative pathogens, only atypical pathogens (ie, *Legionella pneumophila*, *Mycoplasma pneumoniae*, or *Chlamydophila pneumoniae*), a mixture of both Gram-positive and Gram-negative pathogens, a mixture of Gram-positive and atypical pathogen, or a mixture of Gram-negative and atypical pathogens will be summarized by treatment group overall (microITT and ME-PTE populations) and by PORT Risk Class and geographic region for the microITT and ME-PTE populations.

The number and percentage of subjects with a positive blood culture by pathogenic organism will be provided for the microITT and ME populations. The number and percentage of subjects with a Gram-positive organism (aerobes and anaerobes) and with a Gram-negative organism (aerobes and anaerobes) will be presented by genus and species. The percentage of subjects with a positive blood culture by pathogenic organism will be provided for the microITT population by geographic region.

A listing will be provided that includes all baseline and post-baseline isolates obtained from the blood, respiratory specimen, UAT, and serology and will indicate the type of specimen, testing modality, and pathogenic organism.

Several tables providing the minimum inhibitory concentration (MIC) data for the pathogens identified from the baseline blood and respiratory cultures will be provided for the microITT and ME populations:

- The MIC distribution to omadacycline and moxifloxacin, across treatment groups
- The MIC distribution to the test article received, by treatment group

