A concordance analysis of the primary efficacy outcome (Early Clinical Response at 72 to 120 hours) with the overall assessment of Clinical Response at the PTE Visit (based on the investigator's assessment) will be conducted in the ITT population. A concordance analysis of overall assessment of Clinical Response (based on the investigator's assessment) and microbiological response at the PTE Visit will be conducted in the microITT population.

The number and percentage of subjects with an Early Clinical Success (microITT population) with an assessment of Clinical Success (based on the investigator's assessment) at the EOT Visit (microITT and ME-EOT populations), and with an overall assessment of Clinical Success at the PTE Visit (based on investigator's assessment, for the microITT and ME-PTE populations), will be tabulated by baseline MIC to omadacycline and moxifloxacin by pathogen (for those pathogens occurring at least 5 times in one of the treatment groups) and treatment group.

Microbiological Outcomes

The per-subject microbiological response at the EOT and PTE Visits in the microITT, ME-EOT (EOT Visit only), and ME-PTE (PTE-Visit only) populations will be determined to support the clinical findings. The number and percentage of subjects classified with a favorable (eradication and presumed eradication) and unfavorable (persistence, presumed persistence) and indeterminate microbiological response (by definition, indeterminates are excluded from the ME populations) will be tabulated for both treatment groups. A 2-sided 95% CI without stratification will be constructed for the observed difference in the per-subject favorable microbiological response rate between the omadacycline and moxifloxacin groups using the method of Miettinen and Nurminen (1985).

Per-subject microbiological response at the PTE Visit in the microITT and ME-PTE populations will also be provided for infections caused by monomicrobial and polymicrobial Gram-positive or Gram-negative pathogens, only atypical pathogens, a mixture of both Gram-positive and Gram-negative pathogens, a mixture of Gram-positive and atypical pathogens, or a mixture of Gram-negative and atypical pathogens.

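### In the two SAP outputs that show MICs to both drugs, the rule for duplicate baseline isolates ranks on a different drug in each arm

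*Combined protocol and SAP*

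**What the plan says.** SAP 6.1.3 deals with several specimens of one testing modality at one time point that grow the same pathogen: "only the pathogen with the highest MIC to the test article received will be used". Ties are broken without reference to treatment: "If the pathogens have the same MIC to the test article received, the pathogen with the lowest accession number will be used". The Gram stain follows the isolate kept: "The Gram's stain associated with the selected pathogen will be utilized for analysis". When blood and a respiratory sample yield the same pathogen, the same ranking applies, but only to some tables: "for tables providing MIC or disk diffusion data, the pathogen with the highest MIC to the test article received will be used".

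Baseline MICs then feed two kinds of output.

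- **Received-drug outputs:** the MIC distribution, the MIC range with MIC50 and MIC90, and disk zone diameters, each for the drug received (SAP 9.2.1); and decreasing susceptibility, a 4-fold rise in the MIC of the drug received (SAP 10.4).
- **Two-drug outputs:** "The MIC distribution to omadacycline and moxifloxacin, across treatment groups" (SAP 9.2.1), and clinical success rates, which "will be tabulated by baseline MIC to omadacycline and moxifloxacin by pathogen" and treatment group (SAP 10.4), for pathogens occurring at least 5 times in one arm.

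The SAP gives no other selection rule for the two-drug outputs.

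**The concern.** A baseline characteristic should be fixed without using the treatment. Here the wording is the same for both arms, but the drug it ranks on is not. The pooled omadacycline MIC distribution combines, for subjects with duplicates, the highest omadacycline MIC from the omadacycline arm with the omadacycline MIC of an isolate chosen on moxifloxacin from the other arm. The moxifloxacin distribution mirrors this. In the table of success by baseline MIC, a subject's row for a given drug can depend on the arm. Cells there may be small, so one or two moved subjects could change how a row reads.

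There is also a gap. MicroITT is a subset of ITT, and ITT keeps randomised subjects who were never dosed (SAP 6.1.1 and 6.1.3). SAP 8.2 expects such subjects to have baseline pathogens, since it gives them a study day for pathogen determination. For them there is no drug received to rank on.

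**Working it through.** No sample size, power or alpha figure in the plan depends on this rule, so there is no stated figure to reproduce. The check is of the text, followed by an illustration of size.

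**Step 1: one subject.** Take two isolates of one species. Isolate A has an omadacycline MIC one dilution above B's; B has a moxifloxacin MIC one dilution above A's. If the subject received omadacycline, A is kept. If the subject received moxifloxacin, B is kept. The omadacycline MIC recorded at baseline is then one dilution lower solely because of the treatment.

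**Step 2: average size, simple case (assumption).** Let each isolate's log2 MIC vary by -1, 0 or +1 dilution with probabilities 0.25, 0.5 and 0.25, independently between isolates and between drugs.

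- The difference D of two isolates is 0 with probability 6/16, ±1 with 4/16 each, and ±2 with 1/16 each.
- E|D| = (8 × 1 + 2 × 2)/16 = 12/16 = 0.75.
- The expected maximum of two is half of this, 0.375 dilution above the mean.
- Selection on an unrelated drug gives 0.
- Gap between arms: 0.375 dilution.

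**Step 3: range (assumption).** Let log2 MIC have an SD of 1 dilution, correlation ICC between a subject's two isolates, and correlation ρ between the two drugs. Selection on the drug itself raises the mean by √((1 − ICC)/π); selection on the other drug raises it by ρ times that. The gap is (1 − ρ) × √((1 − ICC)/π):

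| ICC | ρ = 0 | ρ = 0.5 | ρ = 1 |
|---|---|---|---|
| 0 | 0.56 | 0.28 | 0 |
| 0.5 | 0.40 | 0.20 | 0 |
| 0.9 | 0.18 | 0.09 | 0 |

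A simulation of 400,000 subjects per arm, with identical isolate distributions in both arms, agrees to within 0.005. At ρ = 0, the share of retained isolates above the single-isolate 95th percentile for moxifloxacin is 6.7% (ICC 0.9) to 9.8% (ICC 0) in the moxifloxacin arm, against 5.0% in the omadacycline arm.

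**Step 4: dilution across the table.** Suppose a fraction f of subjects with an MIC have duplicates, equally in both arms. The mean gap between arms is f × gap. The pooled mean differs from that under an arm-neutral highest-MIC rule by half of this. With the 0.375 gap and f from 5% to 20% (assumption):

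- between arms: 0.05 × 0.375 = 0.019 to 0.20 × 0.375 = 0.075 dilution;
- pooled: 0.009 to 0.038 dilution.

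**Step 5: after the change.** If the highest MIC to the tabulated drug is used in both arms, the gap is 0 by construction when the isolate populations are the same.

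**The case against.** The strongest case for the plan is that most of its MIC outputs concern the drug received, and for those the rule is a sensible worst case. That stands, and those outputs should keep it. The affected tables are descriptive, and SAP 10.4 draws no non-inferiority conclusion. That stands too.

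Duplicates are also limited. SAP 6.1.3 accepts a post-dose sputum as baseline only if the first was unobtainable or inadequate, and a later blood sample only if no earlier one was taken or it showed no pathogen. What remains is mainly paired blood culture sets drawn 15 to 30 minutes apart (protocol 16.1.4.3) and blood plus respiratory pairs. Such isolates may well be alike, which puts the likely gap towards the low rows of the table above.

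Four stronger readings are tempting, but the documents do not support them.

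- **Resistance phenotype is always selected differently by arm.** A reader might note that moxifloxacin defines fluoroquinolone resistance ("Fluoroquinolones – moxifloxacin"). With one resistant and one susceptible pneumococcus, the moxifloxacin arm would always keep the resistant one, and the omadacycline arm about half the time if its MICs are unrelated. But SAP 6.1.3 treats these phenotypes as distinct pathogens, and on that wording both isolates are kept. The example works only if the definition in SAP 5.2.2.2 governs ("If a subject has the same pathogen (ie, same genus and species) identified from both a respiratory and blood specimen"). This is an ambiguity, not an established fault.
- **The arms compare differently selected subjects.** The rule drops isolates, not subjects. At most a subject moves to another MIC row.
- **The AUC/MIC breakpoint work is biased.** Protocol 22.12 does not cite these tables. Only omadacycline-treated subjects have omadacycline exposure, and there the rule already ranks on omadacycline MIC.
- **A definite number of subjects is affected.** The 202 expected microITT subjects (SAP 5.1.1) include those identified only by urinary antigen or serology, who have no MIC. No duplicate rate is given.

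**Conclusion.** The point holds in a narrow form. In the two outputs that tabulate MICs to both drugs, the retained baseline isolate depends on the drug received, and the rule selects nothing for untreated microITT subjects. This follows from the text and needs no assumption.

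The size does need assumptions. Among subjects with MIC-discordant duplicates, the gap between arms in the retained MIC is 0 to 0.56 dilution over the range examined. It vanishes if duplicates have identical MICs or if both drugs rank them alike. Spread over a whole table it is a few hundredths of a dilution under the duplicate rates assumed above. It can matter only for individual rows with few subjects. The primary Early Clinical Response analysis and all formal tests are unaffected. This is a minor correction, worth making because it is almost free.

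**What to change.** In SAP 6.1.3:

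1. For the pooled MIC distributions (9.2.1) and for clinical success by baseline MIC (10.4), retain the highest MIC to the drug being tabulated, in both arms and whatever treatment was received. This also covers subjects who were never dosed.
2. Keep the received-drug rule for all received-drug outputs, including decreasing susceptibility, so that its baseline matches its definition.
3. Keep the existing rule for the linked Gram stain. For untreated subjects, the accession-number tie-break can serve.
4. State whether the same pathogen means the same genus and species, as in 5.2.2.2, or the same resistance phenotype. If genus and species, use the lowest accession number in both arms for by-phenotype outcome tables.

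The cost is a short SAP edit and a small programming change. The change is feasible because the central laboratory tests submitted isolates against both drugs (protocol 17.2.2.1). The downside is small: one subject's two tabulated MICs may come from different isolates, which a table footnote should say.

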6.1.4 Clinically Evaluable (CE) Populations

Two CE populations will be defined: the CE-EOT and the CE-PTE. Subjects will be *included* in or *excluded* from the CE analysis sets based on the criteria listed below.

6.1.4.1 Diagnosis of CABP

To be included in the CE-EOT and CE-PTE populations, subjects must meet the following protocol defined inclusion criteria that describe the CABP:

Inclusion Criterion 3: Has at least 3 of the following symptoms:

- Cough
- Production of purulent sputum
- Dyspnea (shortness of breath)
- Pleuritic chest pain.

Inclusion Criterion 4: Has at least 2 of the following abnormal vital signs:

- Fever or hypothermia documented by the investigator (po or rectal temperature $> 38.0^{\circ}\text{C}$ [100.4°F] or $< 36.0^{\circ}\text{C}$ [95.5°F])

- Hypotension with systolic blood pressure (SBP) < 90 mmHg
- Heart rate > 90 bpm
- Respiratory rate (RR) > 20 breaths/minute.

Inclusion Criterion 5: Has at least 1 clinical sign or laboratory finding associated with CABP:

- Hypoxemia Partial pressure of arterial oxygen (PaO₂) < 60 mmHg by arterial blood gas (ABG)
- Physical examination findings of pulmonary consolidation (dullness on percussion, bronchial breath sounds, egophony, rales, rhonchi, or decreased breath sounds)
- An elevated total white blood cell (WBC) count (> 12,000 cells/mm³) **or** leucopenia (WBC < 4,000 cells/mm³) **or** elevated immature neutrophils (> 15% band forms regardless of total peripheral WBC count).

Inclusion Criterion 6: Radiographically-confirmed pneumonia, ie, new or progressive pulmonary infiltrate(s) on chest X-ray (CXR) or chest computed tomography (CT) scan consistent with acute bacterial pneumonia within 24 hours prior to the first dose of test article.

If the imaging study is done more than 24 hours prior to the first dose of test article but within 48 hours, the subject will be included in the CE populations as long as the imaging study shows a new or progressive pulmonary infiltrate(s) consistent with acute bacterial pneumonia.

Inclusion Criterion 7: Have disease categorized as being PORT Risk Class II, III, or IV at Screening:

The Sponsor Medical Monitor will also review those subjects with a concomitant illness identified after baseline that could have presented at baseline as pneumonia. If it is determined that the subject does not have pneumonia but had another condition such as lung cancer at baseline, the subject will not be evaluable for the CE populations.

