12.1 Inclusion Criteria

To be eligible for randomization in this study, a subject must fulfill ALL of the following criteria:

1. Written and signed informed consent must be obtained before any protocol specific assessment is performed.
2. Male or female, aged 18 years or older
3. Has at least 3 of the following symptoms:
 - Cough
 - Production of purulent sputum
 - Dyspnea (shortness of breath)
 - Pleuritic chest pain.
4. Has at least TWO of the following abnormal vital signs
 - Fever or hypothermia documented by the investigator (temperature $> 38.0^{\circ}\text{C}$ [100.4°F] or $< 36.0^{\circ}\text{C}$ [95.5°F])
 - Hypotension with systolic blood pressure (SBP) < 90 mm Hg
 - Heart rate > 90 bpm
 - Respiratory rate (RR) > 20 breaths/minute.
5. Has at least 1 clinical sign or laboratory finding associated with CABP:
 - Hypoxemia (partial pressure of arterial oxygen [PaO_2] < 60 mm Hg by arterial blood gas [ABG] or oxygen saturation $< 90\%$ by pulse oximetry)
 - Physical examination findings of pulmonary consolidation (eg, dullness on percussion, bronchial breath sounds, or egophony)
 - An elevated total white blood cell (WBC) count ($> 12,000$ cells/ mm^3) *or* leucopenia ($\text{WBC} < 4,000$ cells/ mm^3) *or* elevated immature neutrophils ($> 15\%$ band forms, see % bands calculation in [Appendix 4](#), regardless of total peripheral WBC count).
6. Radiographically-confirmed pneumonia, ie, new or progressive pulmonary infiltrate(s) on chest X-ray (CXR) or chest computed tomography (CT) scan consistent with acute bacterial pneumonia within 24 hours prior to the first dose of test article.
7. Has disease categorized as being PORT Risk Class II, III, or IV at Screening (see PORT Risk Class calculation in [Appendix 2](#)).
8. Is expected to require a minimum of at least 3 days of iv therapy for the initial treatment of CABP.
9. Females must have a negative urine pregnancy test at Screening and agree to comply with using an acceptable method of birth control as per your local requirements (eg, abstinence, po contraceptive, intrauterine device [IUD], barrier contraception [condom], tubal ligation, hysterectomy, bilateral oophorectomy, postmenopausal or vasectomized partner) from Screening through post therapy evaluation (PTE). Males must agree to use an acceptable method of birth control with female partner(s) and must not donate sperm from Screening through PTE.

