Appendix 4: Equations and Conversion Factors

1. Cockcroft-Gault equation to calculate creatinine clearance (CrCl) (relevant to Exclusion Criterion number 9):

$$\frac{(140-\text{age}[yrs]) * \text{weight [kg]} * (Z)}{\text{Cr [mg/dL]} * 72}$$

Z = 1.0, if Male
Z = 0.85, if Female

2. $\text{mm}^3 = \mu\text{L}$
3. $\text{cc} = \text{mL}$
4. Conversion of immature neutrophils (bands) in K/ μL or K/mL to % bands (relevant to Inclusion Criterion number 5 and Exclusion Criterion number 11):
 $[(\text{bands K}/\mu\text{L})/(\text{total WBC K}/\mu\text{L})] \times 100 = \% \text{ bands}$
Or
 $[(\text{bands K}/\text{mL})/(\text{total WBC K}/\text{mL})] \times 100 = \% \text{ bands}$
5. Corticosteroid conversions (relevant to Exclusion Criterion number 10):

The following have equivalent glucocorticoid activity ^a	
Hydrocortisone	160 mg
Prednisone	40 mg
Prednisolone	40 mg
Methylprednisolone	32 mg
Triamcinolone	32 mg
Dexamethasone	6 mg

^a Axelrod L. Glucocorticoid therapy. In: Jameson JL & De Groot LJ, eds. Endocrinology. 6th ed. Philadelphia, PA: Saunders; 2010:1840.

6. Blood urea conversion to blood urea nitrogen (BUN) (relevant to PORT Risk Class calculation)

(blood urea in mmol/L)/0.357 = BUN in mg/dL

OR

(blood urea in mg/dL)/2.14 = BUN in mg/dL

ADMINISTRATIVE CHANGES		
Protocol section	Summary of Changes	Rationale
Cover page	Change of Paratek address.	Paratek moved to new corporate offices in Boston, MA and King of Prussia, PA during the summer of 2015.
Section 2.1 Section 3	[name] added as an emergency contact and replaces [name] as Sponsor Signature.	[name] joined Paratek in September of 2015 as Vice President of Clinical and Medical Affairs.
CLARIFICATIONS		
Protocol section	Summary of Changes	Rationale
Section 5, Section 7, Section 8, Section 9.1, Section 11.1	Abbreviation corrections: CK, creatine phosphokinase; PORT, Pneumonia Outcomes Research Team	Corrections.
Section 7	In Inclusion Criterion 1 the text “protocol specific” was added.	To align with the wording of Inclusion Criterion 1 in Section 12.1.
Section 7, Section 12.1, Section 12.2, Section 14.3.1.2	In Inclusion Criterion 4, Exclusion Criterion 11 and Section 14.3.1.2 references to “oral or rectal” as the only acceptable sites of body temperature measurement were removed.	Operational clarification, body temperature measurements at body sites other than oral or rectal are acceptable.

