Appendix 4	Conversion equations from blood urea to blood urea nitrogen (BUN) were added.	Some site's local laboratories report only blood urea, however BUN is required for the calculation of PORT scores.

MODIFICATIONS

Protocol section	Summary of Changes	Rationale
Section 7, Section 8, Section 12.1, Section 14.2, Section 22.6	
Pulse oximetry measurement of oxygen saturation was added as an acceptable method to determine hypoxemia.
 
In Section 7 and Section 12.1 the wording of Inclusion Criterion 5 was changed as follows:
 
Previous wording:
 
 • Hypoxemia (partial pressure of arterial oxygen [PaO_2]) < 60 mm Hg by arterial blood gas (ABG) 
Current wording:
 
 • Hypoxemia (partial pressure of arterial oxygen [PaO_2]) < 60 mm Hg by arterial blood gas [ABG] or oxygen saturation < 90% by pulse oximetry) 
In Section 8 in the Study Flowchart the row heading “PORT Risk Class, ABG” was changed to “PORT Risk Class, ABG or pulse oximetry”.
 
In Section 14.2 the 12th bullet point was changed from “ABG and PORT Risk Class Assessment” to “ABG (or pulse oximetry) and PORT Risk Class Assessment”.
 
In Section 22.6 “PaO_2 (> 60 mm Hg by ABG)” was changed to “PaO_2 (\geq 60 mm Hg by ABG or oxygen saturation \geq 90% by pulse oximetry)”
	The original PORT study allowed for pulse oximetry as an acceptable alternative to ABG (Fine et al. 1997, NEJM).
Section 7, Section 12.1	
Inclusion Criterion 9:
 
Previous wording:
 
“Females must have a negative urine pregnancy test at Screening and agree to comply with using a highly effective form of birth control (eg, abstinence, po contraceptive, intrauterine device [IUD], barrier contraception [condom], tubal ligation, hysterectomy, bilateral oophorectomy, or vasectomized partner) from Screening through post therapy evaluation (PTE). Males must agree to use a highly effective method of birth control with female
	
A “highly effective method” changed to “an acceptable method” because of different regional definitions of highly effective methods of birth control.
 
Postmenopausal added as a method of birth control.

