Baseline assessments of clinical symptoms, clinical signs, abnormal vital signs, and abnormal laboratory signs of CABP will be presented for the ITT, Safety, microITT, and CE-PTE populations. The number and percentage of subjects with each of the CABP symptoms (cough, pleuritic chest pain, dyspnea, and phlegm/sputum production) by severity (absent, mild, moderate, severe) will be presented by treatment group. The number and percentage of subjects with the presence by severity (ie, absent, mild, moderate, severe) of the following clinical signs will be provided by treatment group: rales, rhonchi, dullness on percussion, bronchial breath sounds, wheezing, decreased breath sounds, and egophony. The number

and percentage of subjects with fever (defined as body temperature $> 38^{\circ}\text{C}$ [100.4°F] oral or rectal), hypothermia (defined as body temperature $< 36^{\circ}\text{C}$ [95.5°F] oral or rectal), hypotension with systolic blood pressure $< 90 \text{ mmHg}$, heart rate $> 90 \text{ bpm}$, respiratory rate $> 20 \text{ breaths/min}$, hypoxemia (defined as $\text{PaO}_2 < 60 \text{ mmHg}$ by arterial blood gas or oxygen saturation $< 90\%$ by pulse oximetry), elevated total WBC count ($> 12,000 \text{ cells/mm}^3$), leucopenia (WBC $< 4,000 \text{ cells/mm}^3$), elevated immature neutrophils ($> 15\%$ band forms regardless of total peripheral WBC count) and any of elevated total WBC count, leucopenia or elevated immature neutrophils will be summarized by treatment group. Differences between treatment groups will be tested for statistical significance using Fisher's exact test.

Risk factors for CABP will be presented by treatment group for the ITT, Safety, microITT, and CE-PTE populations. Risk factors include smoking (current, past, and descriptive statistics of the number of years since quitting for those subjects who were previous smokers), receipt of pneumococcal vaccine, prior lung infection, whether the subject had mild to moderate COPD, symptomatic asthma with wheezing, and chronic cough with or without sputum production. Differences between treatment groups will be tested for statistical significance using Fisher's exact test for categorical variables and the Wilcoxon rank sum test for continuous variables. Other medical and surgical history will be summarized based on MedDRA system organ class by treatment group for the ITT and Safety populations.

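### SAP 6.1.4.1 restates the CE hypoxemia criterion in superseded protocol wording (blood gas only), although protocol version 2.0 and the rest of the SAP also accept pulse oximetry

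*Combined protocol and SAP*

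**What the plan says.** SAP 6.1.4.1 sets the diagnostic entry conditions for both CE populations: "To be included in the CE-EOT and CE-PTE populations, subjects must meet the following protocol defined inclusion criteria that describe the CABP". Under Criterion 5 it gives hypoxemia as PaO2 below 60 "mmHg by arterial blood gas (ABG"), with no alternative. Under Criterion 4 it limits temperature by site: "Fever or hypothermia documented by the investigator (po or rectal temperature".

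Protocol version 2.0 (27-OCT-2015), Section 12.1, reads differently on both items. Hypoxemia may be shown "by arterial blood gas [ABG] or oxygen saturation" below 90% by pulse oximetry. The temperature item has no site limit: "Fever or hypothermia documented by the investigator (temperature". The version 2.0 summary of changes shows that both edits were intended: "Pulse oximetry measurement of oxygen saturation was added as an acceptable method to determine hypoxemia", and "body temperature measurements at body sites other than oral or rectal are acceptable".

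The SAP is Final 1.0, dated 17-MAR-2017, about 17 months after version 2.0. Its Section 7, on departures from the protocol, lists only the added expanded microITT population.

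**The concern.** The SAP presents the list as the protocol's own, but one item is narrower than the protocol under which later subjects were enrolled. A subject who entered under version 2.0 with low saturation on oximetry, no qualifying blood gas and no other Criterion 5 finding met the protocol. Read as printed, the SAP would exclude that subject from CE-EOT and CE-PTE for failing it. SAP 6.1.5 builds the ME populations from the CE populations, so the exclusion carries through.

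The SAP would also treat the same subject in two ways: hypoxemic in the baseline table of Section 9.2 and not hypoxemic for CE entry. What is at stake is whether a stated population rule matches its source and can be programmed without a judgement call. The primary result is not at stake.

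**Working it through.** The documents state no figure for the number affected, so the main check is a comparison of texts.

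**1. Hypoxemia, place by place**

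| Place | Blood gas | Pulse oximetry |
|---|---|---|
| Protocol v1.0, 12.1, Criterion 5 | yes | no |
| Protocol v2.0, 12.1, Criterion 5 | yes | yes, below 90% |
| SAP 6.1.4.1 (CE entry) | yes | **no** |
| SAP 9.2, baseline hypoxemia | yes | yes ("by arterial blood gas or oxygen saturation" below 90%) |
| SAP 9.2, modified ATS severity | yes | saturation below 90% accepted |
| SAP 10.4, stabilization at 72 to 120 hours | yes | yes |

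Only SAP 6.1.4.1 agrees with version 1.0. SAP Appendix 1 also keeps the version 1.0 flowchart row that pairs PORT class with blood gas alone, where the version 2.0 flowchart adds oximetry. Carry-over is therefore the likely explanation. The summary of changes is used here only to show intent; the conflict is between the current SAP and the current protocol.

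**2. Who could be lost**

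A subject fails the printed Criterion 5 but passes version 2.0 only if all of these hold:
- saturation is below 90% by oximetry;
- there is no PaO2 below 60 mmHg by blood gas;
- none of the listed chest findings is present;
- there is no qualifying white-cell or band abnormality.

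SAP 6.1.4.1 names six chest findings: dullness, bronchial breath sounds, egophony, rales, rhonchi and decreased breath sounds. Version 2.0 gives the first three as examples. The longer list makes the third condition harder to meet in subjects who also have a radiographic infiltrate. The count cannot be derived from the documents.

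**3. Temperature**

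The site limit in 6.1.4.1 also differs from version 2.0, but no effect can be shown. Protocol 16.1.2 does not ask for the measurement site to be recorded, so the limit may not be programmable. SAP 9.2 defines baseline fever and hypothermia with the same oral or rectal limit, although its SIRS definition allows an oral equivalent.

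**4. Size under assumed losses**

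Inputs:
- 750 randomized, and 85% success in both arms (SAP 5.1.1).
- 80% evaluability. SAP 5.1.1 applies this to the 638 PORT III/IV subjects: 0.80 × 638 = 510.4, the plan's 510. CE-PTE in this SAP includes PORT II, so extending 80% to all 750 is an assumption: 0.80 × 750 = 600, or 300 per arm.
- Losses of 2%, 5% and 10% are assumptions without a source in the documents.

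Method: the unstratified Miettinen-Nurminen 95% interval of SAP 10.1, with observed difference 0. The limits are the roots in RD of 3.84 = (0 − RD)² / V, where V = [p̃₁(1 − p̃₁)/n₁ + p̃₂(1 − p̃₂)/n₂] × (n₁ + n₂)/(n₁ + n₂ − 1).

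| Assumed loss | CE-PTE total (per arm) | Half-width, points | Change |
|---|---|---|---|
| 0% | 600 (300) | 5.77 | – |
| 2% | 588 (294) | 5.83 | 0.06 |
| 5% | 570 (285) | 5.92 | 0.15 |
| 10% | 540 (270) | 6.09 | 0.32 |

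**The case against.** **The SAP may set its own evaluability rules.** Protocol 22.1 leaves further CE criteria to the SAP, so a stricter rule is within its remit. That is correct, but 6.1.4.1 does not present its list as a stricter choice. It attributes the list to the protocol, and Section 7 declares no change.

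**The Evaluability Review Team would catch it.** SAP 6.2.1 and 6.2.2 give the team a real part: CE membership is determined programmatically and by its manual review, under a process document not provided here. The team might resolve such a case sensibly. No visible text, however, lets it override a printed criterion.

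**The SAP's intent is evident.** Oximetry is accepted in Sections 9.2 and 10.4, and the old row in Appendix 1 is only a schedule that does not govern CE membership. This stands, and it is why the correction should be uncontroversial. It does not tell a programmer which text to follow.

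**Little or nothing turns on it.** This largely stands. Loss needs an unusual combination of findings, the count may be zero, and the intervals in SAP 10.3 are descriptive with no non-inferiority conclusion.

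A reader might infer that the temperature limit is an equal second fault that would also remove subjects. The documents do not support that: the site is not requested, the summary of changes files the edit as an operational clarification, and SAP 6.1.4.1 and the baseline fever definition in 9.2 agree with each other.

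**Conclusion.** The mismatch on hypoxemia is certain from the text and should be corrected. Its consequence is limited: an unknown, probably small and possibly zero number of version 2.0 enrollees could be dropped from CE and ME if the rule is applied as printed. The widening of the descriptive CE-PTE interval would be about 0.06 to 0.32 points over assumed losses of 2% to 10%, given 85% success in both arms and an assumed base of 600. The FDA primary analysis is untouched.

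A reader might go further and infer that the CE comparison is biased between arms, or that an EMA conclusion is weakened. The documents support neither. Nothing suggests that reliance on oximetry differs by arm. CE at PTE is co-primary for the EMA (protocol 22.4.3), but that analysis belongs to a separate SAP that is not provided, so its CE wording can only be queried.

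**What to change.** Before database lock, in SAP 6.1.4.1, change the hypoxemia item to PaO2 below 60 mmHg by arterial blood gas or oxygen saturation below 90% by pulse oximetry. Bring the CE programming and the Evaluability Review Team instructions into line. If a narrower rule is intended, state and justify it in Section 7 instead.

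As tidying with no demonstrated effect, remove the oral or rectal temperature limits in 6.1.4.1, 6.1.4.6 and 9.2 to match version 2.0. The 6.1.4.6 edit is minor, since those exclusions rest on what the investigator documented in the eCRF. Also confirm that the separate EMA SAP uses the version 2.0 hypoxemia wording.

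The cost is a few wording edits plus matching programming and instructions, with no new data. Changing CE membership after unblinding would be harder to defend.
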